Evaluation of Hemorrhage Control and Tourniquet Training Effectiveness for Laypersons: TRIAGE
Study (**TouRnIquet trAininG Effectiveness**)

April 3, 2018
Study Protocol and Statistical Analysis

- 1) **Study design:**
 - a) Prospective open-label trial

- 2) **Consent:**
 - a) Verbal consent

- 3) **Protocol:**
 - a) All participants will receive the ACS stop the Bleed training from qualified instructors. This training is 45 to 60 minutes long, consisting of an audio-visual presentation with tourniquet application instructions followed by hands-on training under the supervision of an instructor. The training takes place in groups of 20 to 50 at a time. The audio-visual part of the training takes place in groups of 20, which are then divided into subgroups of 4-8 for hands-on training with an instructor. There is no compensation for the study participants.
 - b) The evaluation of hemorrhage control competence will take place individually. A mannequin, the Hapmed tourniquet trainer, with a traumatic amputation of the leg just above the knee will be present. A reviewer will provide instructions, including that the lights on the leg represent continued bleeding and they will have a maximum of 2 minutes to apply the tourniquet. The participant will be provided a tourniquet and told to stop the simulated bleeding. Participants will be tested in all 5 types of tourniquets sequentially using the same method but with the order of testing varying according to the randomization. The reviewer will start timing after telling the participant to begin. This will then be repeated for the other type of tourniquet the individual will need to apply. No feedback will be given to the participant throughout the testing process.
 - i) Supplies for the improvised tourniquet will include a T-shirt, long stretch of gauze, a stick to act as a windlass, and a leather belt
 - c) Parameters measured:
 - i) The participants will be timed until they feel that they have stopped the bleeding or they tell the instructor they are done. The maximum amount of time provided to apply the tourniquet will be 2 minutes based on the results of the investigators' prior studies in which the 90th percentile for time to correct application was 117 seconds.
 - ii) Appropriateness of hemorrhage control will be determined by correct placements of tourniquet as defined by at least 2 inches proximal to the amputation site
 - iii) Adequate pressure to stop the bleeding which will be set at 250 mmHg. For unsuccessful hemorrhage control, the reason for failure will be recorded.
 - iv) Correct tourniquet application defined by:
 - (1) Time to application < 120 seconds
 - (2) Placement of tourniquet a minimum of 2 inches proximal to amputation
 - (3) Tourniquet application pressure > 250 mmHg
 - d) All the reviewers would be physicians, nurses and EMTs, trained in hemorrhage-control. The complete test for each individual will not take more than 15 mins.

- 4) **Randomization for the order of tourniquet application:**
 - a) Permutated block randomization will be used to vary the order for application of the 5 different types of tourniquets (CAT, RAT, SWAT-T, Sof-T, and improvised tourniquet)

5) Pre-trial questionnaire:

- a) Study subjects will be given a pre-trial questionnaire to gather information regarding age, gender, and level of education. The questionnaire will also include questions to assess their knowledge regarding hemorrhage control and to determine their willingness and self-reported comfort level in acting as a first-responder in a mass casualty scenario. Answers will be presented on a Likert-type scale or dichotomous yes-no.

6) Post-trial questionnaire:

- a) After the hemorrhage control training, all participants will be given a questionnaire to evaluate comfort level, self-efficacy, and other questions relating to hemorrhage control response.

7) Sample size calculation:

- a) Sample Size calculation was done for paired comparisons with 80% power and Bonferroni corrected for 4 pairwise comparisons for an alpha level of 0.0125 and correlation of 0.1. The largest difference was then taken as the sample size for each arm.
- b) The expected corrected proportions for the different tourniquets are:
 - (1) CAT: 80-90% (Control)
 - (2) RAT: 10-30%
 - (3) SWAT-T: 10-30%
 - (4) Sof-T: 20-40%
 - (5) Improvised: < 10%
- ii) The smallest presumed difference in correct application for the CAT (control) at 80% is to the Sof-T at 40%. To attain 80% power with alpha of 0.0125 the required minimum sample size is 34.
- c) All sample size calculations performed using Stata v14.1.

8) Statistical Analysis:

- a) Paired statistical tests using McNemars test will be used for the univariate analysis of the primary outcome of correct tourniquet application comparing the CAT tourniquet as a control (CAT being type of tourniquet taught in the B-Con course) to each of the other tourniquet types (RAT, SWAT-T, Sof-T, Improvised) for 4 total pairwise comparisons.
- b) Descriptive statistical analysis (ANOVA, Kruskal-wallis, Mann Whitney U test, Student T-test) will be used to assess the secondary outcomes of time to tourniquet application, estimated blood loss prior to tourniquet application, and pressure applied by the tourniquet.
- c) Multiple Logistic regression will be used to assess for predictors of correct tourniquet application for each of the different tourniquet types. The model will include age, gender,

education level, any prior hemorrhage control training, and success in application for each of the other tourniquet types.

- d) Descriptive statistics will also be used to assess participants responses on the questionnaires. Non-parametric statistical tests (Wilcoxon signed rank test and generalized estimating equations) will be used to assess 5-point Likert scale questions.
- e) P-value for significance will be set at 0.05 after Bonferroni correction.

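### Section 8b names no paired test although every participant applies all five devices, and its time outcome mixes correct with incorrect applications

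*Combined protocol and SAP*

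**What the plan says.** **Design.** Section 3b: "Participants will be tested in all 5 types of tourniquets sequentially using the same method". Device order is randomised (section 4), so every participant contributes a result on each device.

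**Time.** Section 3c-i stops the clock on the participant's own judgement: "The participants will be timed until they feel that they have stopped the bleeding or they tell the instructor they are done". The limit is 2 minutes. During the test, "the lights on the leg represent continued bleeding", and no feedback is given.

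**Correct application.** Section 3c-iv defines this separately by three criteria: "Time to application < 120 seconds", placement at least 2 inches proximal, and pressure above 250 mmHg. Section 3c-iii adds: "For unsuccessful hemorrhage control, the reason for failure will be recorded".

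**Analysis.** For the primary outcome, section 8a says: "Paired statistical tests using McNemars test will be used for the univariate analysis of the primary outcome of correct tourniquet application". For the three secondary outcomes (time, estimated blood loss, pressure), section 8b calls the analysis descriptive and lists ANOVA, Student's t, Kruskal-Wallis and Mann-Whitney. It does not name the groups to be compared, mention pairing, or say how unsuccessful attempts enter the time analysis. Wilcoxon signed-rank and generalized estimating equations appear in section 8d, for the Likert items only.

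**The concern.** There are two separate issues.

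*Pairing.* Kruskal-Wallis and Mann-Whitney are independent-sample tests. ANOVA and the t-test have repeated-measures and paired forms, but section 8b does not ask for them. Comparing devices is the likeliest purpose of section 8b, and for that purpose independent-sample tests ignore that the same people supply every group. Their standard errors, and hence their p-values, are wrong unless a person's results on different devices are uncorrelated.

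*Meaning of the time.* Declared completion is recorded whether or not the device was placed correctly and tight enough. If success rates differ between devices as section 7b expects, CAT times are mostly times to success and comparator times mostly times to stopping without success. Someone who reads a shorter time as faster correct application would be misled.

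**Working it through.** **1. The plan's own figure.** Section 7 uses CAT 80%, Sof-T 40%, 80% power, and "alpha level of 0.0125 and correlation of 0.1".

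- P(both correct) = 0.8 × 0.4 + 0.1 × √(0.8 × 0.2 × 0.4 × 0.6) = 0.3396.
- Discordant probabilities: 0.8 − 0.3396 = 0.4604 and 0.4 − 0.3396 = 0.0604. Their sum is 0.5208 and their difference 0.40.
- McNemar, two-sided: n = [2.498 × √0.5208 + 0.842 × √(0.5208 − 0.16)]² / 0.16 = 33.3, rounded up to 34.

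The stated 34 is reproduced, and the plan's own calculation is a paired one.

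**2. Cost of ignoring the pairing.** With common variance σ² and within-participant correlation ρ, the variance of the mean difference between two devices is 2σ²(1 − ρ)/n. An unpaired analysis uses 2σ²/n. The ratio of standard errors is 1/√(1 − ρ). The documents give a correlation (0.1) for the binary outcome only, so the values of ρ below are assumptions. The level and power columns come from a simulation of 20,000 trials with normal data, n = 34, nominal level 0.0125 and an assumed shift of 0.6 SD.

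| ρ | SE ratio | True level, unpaired t | Power, unpaired t | Power, paired t |
|---|---|---|---|---|
| 0.1 | 1.05 | about 0.008 | 0.47 | 0.50 |
| 0.3 | 1.20 | about 0.003 | 0.46 | 0.62 |
| 0.5 | 1.41 | about 0.001 | 0.45 | 0.79 |

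A five-group ANOVA at nominal 0.05 has a true level of about 0.032, 0.009 and 0.002 at the same three correlations. The loss is small at 0.1 and large at 0.5.

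**3. Whose times are compared.** The rates are those that section 7b introduces with "The expected corrected proportions for the different tourniquets are". Expected correct = 34 × p; expected incorrect = 34 × (1 − p).

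| Device | p | Correct of 34 | Incorrect of 34 |
|---|---|---|---|
| CAT | 0.8-0.9 | 27.2-30.6 | 3.4-6.8 |
| Sof-T | 0.2-0.4 | 6.8-13.6 | 20.4-27.2 |
| RAT, SWAT-T | 0.1-0.3 | 3.4-10.2 | 23.8-30.6 |
| Improvised | below 0.1 | below 3.4 | above 30.6 |

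**4. Pairs that compare success with success.** Using the step 1 formula with correlation 0.1 and the CAT at 0.8-0.9, the expected number of pairs with both applications correct is 6.0-12.7 for the Sof-T and 3.1-9.6 for the RAT and SWAT-T. Pairs with the CAT correct and the comparator incorrect number 34 × (CAT rate − P(both correct)): 15.7-24.1 for the Sof-T and 18.4-27.2 for the RAT and SWAT-T. Whatever the correlation, both-correct pairs cannot exceed 34 × p for the comparator: 13.6, 10.2 and 3.4 (improvised). So at least 20 of the 34 pairs in each CAT comparison are expected not to compare two successes.

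**5. What cannot be computed.** The documents give no times for failed attempts. Participants may give up early, or the lights may keep them trying up to the limit. Neither the direction nor the size of any distortion follows.

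**The case against.** The strongest reply has four parts.

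*Section 8b is descriptive and does not say that devices are compared.* It is true that the groups are not named, and a two-group test could contrast correct with incorrect attempts. But the section lists four hypothesis tests, section 8e sets a significance level, and the trial exists to compare devices. The point is conditional on that reading, which is the likeliest one.

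*ANOVA and the t-test can be run in paired form.* They can, but the plan does not say so, and the two rank tests listed cannot.

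*Unpaired tests only err on the safe side.* This stands for positive correlation. A reader might infer that section 8b risks false-positive findings. Nothing in the documents supports that: the only correlation given is positive, and the consequence is lost power. At 0.1 the loss is slight.

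*Analysing declared time for every attempt is legitimate.* This also stands. It uses complete data, does not condition on success (itself a result of the device), and leaves success to the primary outcome. A reader might infer that the time comparison is biased for or against the CAT, or that it must be replaced by time to correct application with failures ranked worst. The first cannot be shown, because failure times are not given. The second trades one problem for another. I simulated signed-rank tests with failures set at 120 s, correlation 0.1, and correct times drawn from the same distribution for both devices (assumed uniform, 40-119 s). At the 0.0125 level they rejected about 54%, 82% and 97% of the time for CAT 80% against 40%, 30% and 20%, with no difference in speed among successes. Such a test largely repeats the primary outcome. It does not strictly rank failures worst either: a success at 117 s against a failure at 120 s counts as a difference of only 3 s.

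**Conclusion.** The point holds as an omission in the secondary analysis. Section 8b names no paired or repeated-measures method for paired data, in contrast to sections 7a and 8a, and this affects all three of its outcomes. If independent-sample tests are used to compare devices, standard errors are overstated by 5%, 20% or 41% at assumed correlations of 0.1, 0.3 or 0.5.

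The time outcome also needs an interpretive safeguard. On the plan's rates, most CAT times belong to successes and most comparator times to failures, so declared time does not measure speed of correct application. This rests on the section 7b rates and n = 34; it is a statement about what is being compared, not an estimate of bias.

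A reader might infer that the main result is in doubt. It is not: the primary analysis is paired, a time-out already counts as not correct, and the sample size of 34 reproduces.

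**What to change.** In section 8b:

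1. For time, estimated blood loss and pressure, replace the independent-sample tests with paired or repeated-measures ones. For example, use Friedman or repeated-measures ANOVA across the five devices, and Wilcoxon signed-rank or a paired t-test for the four CAT-versus-device comparisons at 0.0125 (0.05/4).
2. Name the time outcome *time to declared completion*. Report it for each device, split by correct and incorrect application under section 3c-iv, as a descriptive summary. The both-correct pairs are too few for a useful separate test.
3. State that a shorter declared time in incorrect attempts will not be interpreted as an advantage.

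A worst-rank analysis with failures at 120 s may be added only as supportive. If it is, state how pairs with both applications incorrect are handled. On the plan's rates these number 34 × (1 − CAT rate − comparator rate + P(both correct)), for example 34 × (1 − 0.8 − 0.4 + 0.3396) = 4.7 for the Sof-T.

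Items 1 to 3 cost wording only: time, placement, pressure and reason for failure are already recorded, and no extra participants are needed. The supportive analysis would add a new outcome definition and should be labelled as such.

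### Does leaving the order set and block size unstated, and test position out of the analysis, weaken the CAT comparisons?

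*Combined protocol and SAP*

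**What the plan says.** Section 3b has every participant "tested in all 5 types of tourniquets sequentially using the same method but with the order of testing varying according to the randomization". Section 4a gives the method: "Permutated block randomization will be used to vary the order for application of the 5 different types of tourniquets". It names the five devices but gives no list of sequences and no block size, and it does not say that each device appears equally often in each position.

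For the analysis, section 8a states that "Paired statistical tests using McNemars test will be used for the univariate analysis of the primary outcome", with CAT compared with each of the other four devices. The logistic models in section 8c adjust for age, gender, "education level, any prior hemorrhage control training, and success in application for each of the other tourniquet types". Test position is in neither, nor in the tests of section 8b.

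Three statements bear on whether position could matter. Section 3b says "No feedback will be given to the participant throughout the testing process", and section 3d says "The complete test for each individual will not take more than 15 mins". But participants are also told that "the lights on the leg represent continued bleeding", and section 8a describes CAT alone as taught: "CAT being type of tourniquet taught in the B-Con course".

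**The concern.** In a five-period within-person design, order is the main nuisance factor. Section 4a can be read in at least three ways:

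1. an independent random order for each person;
2. permuted blocks made from all 120 possible orders;
3. permuted blocks of a small balanced set, such as a Latin square or the 10 Williams sequences.

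Only the third balances position closely with 34 people. Under the other two, CAT may by chance be tested earlier or later on average than a comparator. If people improve or tire over the five attempts, that imbalance adds noise to the difference, and nothing in section 8 removes it. Improvement is conceivable: the lights act as a form of feedback, and four of the five devices are not named as taught. At stake would be the precision of the four CAT comparisons and the chance to report whether success changes with practice.

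**Working it through.** **The plan's own figure.** Section 7 gives CAT 0.80, Sof-T 0.40, correlation 0.1, alpha 0.05/4 = 0.0125, power 80% and n = 34. Sidedness is not stated; two-sided is used here.

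- Both succeed: 0.80 × 0.40 + 0.1 × √(0.8 × 0.2 × 0.4 × 0.6) = 0.3396.
- Discordant cells: 0.80 − 0.3396 = 0.4604 and 0.40 − 0.3396 = 0.0604, which sum to 0.5208.
- n = [2.498 × √0.5208 + 0.842 × √(0.5208 − 0.16)]² / 0.16 = 33.29, rounded up to 34.

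The stated size reproduces, and nothing in it depends on the order scheme.

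**Validity.** With independent random orders, CAT in position i with Sof-T in position j is as likely as the reverse. If the two devices share the same success curve over positions, a discordant pair is equally likely to go either way, which is what McNemar requires. If the curves differ, the expected paired difference is the difference in success averaged over the five positions. So order adds no bias on average.

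**Chance imbalance.** In a random order of five, each position has variance 2 and two positions have covariance −0.5, so their difference has variance 2 + 2 + 1 = 5. The CAT minus Sof-T gap in mean position at n = 34 has standard deviation (SD):

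- independent orders: √(5/34) = 0.38 positions;
- blocks of 120: √(5/34 × 86/119) = 0.33;
- Williams set in blocks of 10: 0.13 (simulated);
- Latin square in blocks of 5: 0.07 (simulated).

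**What the imbalance costs.** This needs a position effect, which the documents do not give. *Assumption:* success changes linearly in log-odds with position, by the same step for every device, and averages 0.80 (CAT) and 0.40 (Sof-T) over positions.

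At a step of 0.4, success over positions 1 to 5 is 0.664, 0.747, 0.815, 0.868, 0.907 for CAT and 0.225, 0.302, 0.392, 0.491, 0.590 for Sof-T. The per-person variance due to position is Var(CAT) + Var(Sof-T) + ½ Cov = 0.0075 + 0.0169 + 0.0055 = 0.030. With independent orders the SD of the difference is 0.1043. Full balance gives √(0.1043² − 0.030/34) = 0.1000, a fall of 4.1%.

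Simulation at n = 34 (alpha 0.0125, asymptotic McNemar):

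| Step | Sof-T, 1st to 5th test | SD, independent | SD, blocks of 120 | SD, Williams | Power, independent | Power, Williams |
|---|---|---|---|---|---|---|
| 0 | 40% to 40% | 0.1029 | – | 0.1029 | 86.0% | 85.9% |
| 0.2 | 31% to 50% | 0.1033 | – | 0.1027 | 85.7% | 85.7% |
| 0.4 | 23% to 59% | 0.1043 | 0.1034 | 0.1005 | 84.9% | 85.7% |
| 0.6 | 16% to 67% | 0.1059 | 0.1032 | 0.0973 | 83.6% | 85.2% |

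- Williams against independent orders: 0.1027/0.1033, 0.1005/0.1043 and 0.0973/0.1059 give −0.6%, −3.6% and −8.1%.
- Williams against blocks of 120: 0.1005/0.1034 and 0.0973/0.1032 give −2.8% and −5.7%.
- If section 4a already means a balanced set, the gain is zero.
- If CAT success does not change with position and only the other devices do, full balance gives −0.6%, −2.4% and −4.8%.

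**Limits of the power figures.** They hold for rates averaged over positions and for the asymptotic test. If 80% and 40% are instead middle-position rates, average success at a step of 0.4 is 78.5% and 40.7%, and power is about 79% with either kind of order. That drop comes from a smaller true difference. The exact McNemar test gives 77.8% with no position effect at all, so that shortfall is a matter of test version.

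**The case for a change.** The best case for acting is that it costs little: one list, one recorded variable and one supporting model, with no extra participants. Two statisticians could build materially different lists from section 4a. If learning is strong, balance is worth several people: at a step of 0.6, 34 × (0.1059/0.0973)² = 40.3, so 34 people in Williams order do the work of about 40 in independent order. A position-adjusted 98.75% interval would also narrow, from a half-width of 27.5 to 26.5 points at a step of 0.4.

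What stands is that the sequence set is unstated and position is unused. The rest is weaker.

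- The gain of six people needs Sof-T success to go from 16% to 67% within one sitting of at most 15 minutes without feedback. At a step of 0.2 the same calculation gives 34.4 people.
- The narrower interval is measured against an interval that section 8 does not contain; the plan tests with McNemar.
- McNemar ignores the balance, so it turns conservative under strong position effects. At a step of 0.6 with equal rates of 0.60, its type I error is 0.011–0.012 with independent orders but 0.004–0.008 with Williams orders, against a nominal 0.0125.
- A second, adjusted result would disagree with McNemar on significance in 1.2% to 5.3% of simulated trials over steps 0 to 0.6. For the improvised device, at an assumed 5% success, its 98.75% interval covers 97.9–98.3%.

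**Conclusion.** No change follows. The missing sequence set and block size are details that must be settled when the list is generated, and each of the three readings gives a valid, on-average unbiased CAT comparison with n = 34 unaffected. If the assigned orders are followed, the list also fixes each attempt's position, so analysts can tabulate success by position without a new analysis plan.

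The possible gain from a balanced set is nil with no position effect. It is about 1%, 3–4% and 6–8% in the SD of CAT minus Sof-T at steps of 0.2, 0.4 and 0.6, and nil again if a balanced set is already meant. The change in McNemar power is at most 85.2 − 83.6 = 1.6 points in the cases above.

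These sizes rest on an assumed linear log-odds effect common to all devices and on rates averaged over positions. Carry-over from one particular device to the next was not modelled, and the documents give no figure for it.

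### Section 8b names no paired or repeated-measures test for time, blood loss and pressure, although every participant contributes all five measurements

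*Combined protocol and SAP*

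**What the plan says.** On the design, section 3b states: "Participants will be tested in all 5 types of tourniquets sequentially using the same method". Section 4a randomises only the sequence: "Permutated block randomization will be used to vary the order for application of the 5 different types of tourniquets". There are no parallel groups.

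The secondary outcomes in section 8b are "time to tourniquet application, estimated blood loss prior to tourniquet application, and pressure applied by the tourniquet". For these the plan states: "Descriptive statistical analysis (ANOVA, Kruskal-wallis, Mann Whitney U test, Student T-test) will be used to assess the secondary outcomes". It does not name the factor being compared, pair any test with any outcome, or mention a participant effect.

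Elsewhere the plan does allow for the repeated measurements:

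- Section 7a sizes the study for paired comparisons, with a correlation of 0.1.
- Section 8a: "Paired statistical tests using McNemars test will be used for the univariate analysis of the primary outcome of correct tourniquet application".
- Section 8d: "Non-parametric statistical tests (Wilcoxon signed rank test and generalized estimating equations) will be used to assess 5-point Likert scale questions".

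**The concern.** Five attempts by one person share that person's strength, dexterity and grasp of the training, so they are likely to be correlated. One-way ANOVA with Kruskal-Wallis for five groups, and the two-sample t-test with Mann-Whitney U for two, treat the attempts as if 5 x 34 = 170 different people had made them. Differences between people then stay in the error term, although a within-participant design exists to remove them.

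For comparisons between tourniquets under positive correlation, the consequences are over-wide intervals, p-values that are too large, and real differences reported as non-significant. All three secondary outcomes are exposed. With a minimum of 34 participants, within-person precision is the main statistical advantage of the design.

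**Working it through.** **Inputs from the documents.** Five tourniquets per participant (3b); order-only randomisation (4a); alpha 0.0125, power 80%, correlation 0.1 for the binary primary outcome (7a); 80% against 40% correct, n = 34 (7b).

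**Assumed inputs.** The documents give no SD or correlation for time, blood loss or pressure. Rho is therefore varied from 0.1 to 0.7, and a 0.5 SD difference is used for illustration. Data are taken as normal with equal variances.

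**1. The plan's own figure.** For paired proportions:

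- p11 = 0.8 x 0.4 + 0.1 x sqrt(0.8 x 0.2 x 0.4 x 0.6) = 0.3396
- Discordant cells: 0.8 - 0.3396 = 0.4604 and 0.4 - 0.3396 = 0.0604. Their sum is pd = 0.5208 and their difference is d = 0.40.
- n = [2.498 x sqrt(0.5208) + 0.842 x sqrt(0.5208 - 0.16)]^2 / 0.16 = 33.29, rounded up to 34.

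The stated 34 is reproduced with a two-sided McNemar calculation. An unpaired two-proportion formula gives 33, so the number alone is weak evidence of pairing; the text of 7a states it directly.

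**2. Standard error of a difference between two tourniquets.**

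- Independent-samples: sqrt(2 sigma^2 / n)
- Correct, paired: sqrt(2 sigma^2 (1 - rho) / n)
- Ratio: 1 / sqrt(1 - rho)

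**3. True type I error of a nominal 5% test.** For the two-sample t-test the large-sample value is 2[1 - Phi(1.960 / sqrt(1 - rho))]. At rho 0.5, 1.960 / 0.7071 = 2.772, which gives 0.56%. The last four columns are simulated at n = 34 (20,000 runs for t and ANOVA, 4,000 for the rank tests).

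| rho | SE ratio | t, formula | t | one-way ANOVA | Kruskal-Wallis | Friedman |
|---|---|---|---|---|---|---|
| 0.1 | 1.05 | 3.9% | 4.0% | 3.2% | 3.7% | 5.2% |
| 0.3 | 1.20 | 1.9% | 2.0% | 1.0% | 1.1% | 4.7% |
| 0.5 | 1.41 | 0.6% | 0.6% | 0.1% | 0.15% | 4.7% |
| 0.7 | 1.83 | 0.03% | <0.1% | <0.1% | about 0 | 4.8% |

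Repeat simulations at rho 0.5 gave 0.6 to 0.8% for the t-test and 0.1 to 0.2% for ANOVA. The within-participant tests hold their level: Friedman as shown, and the paired t-test at about 5% throughout.

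**4. Power for a 0.5 SD difference, n = 34, alpha 0.0125.** Paired t uses the non-central t distribution with 33 degrees of freedom and non-centrality 0.5 x sqrt(34) / sqrt(2(1 - rho)); at rho 0.5 this is 2.915. Independent t is simulated on the same correlated data.

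| rho | Non-centrality | Paired t | Independent t |
|---|---|---|---|
| 0.1 | 2.17 | 33.5% | 31% |
| 0.3 | 2.46 | 44% | 28% |
| 0.5 | 2.92 | 61% | 25% |
| 0.7 | 3.76 | 86% | 21% |

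The rank tests behave alike. For a 0.6 SD difference at rho 0.5, simulated power is 41% for Mann-Whitney and 75% for Wilcoxon signed rank.

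**The case against.** Section 8b is a loose list. ANOVA and the t-test both have within-participant forms, and the authors may have meant those, or may have meant comparisons between people, for example by prior training. Summaries for each tourniquet, such as means, medians and SDs, do not depend on pairing. The only correlation in the plan is 0.1, where the loss is slight. The 0.5 SD difference is not from the plan either: 80% against 40% correct corresponds, on an assumed normal latent scale, to 0.842 + 0.253 = about 1.1 SD. At 1.0 SD and alpha 0.0125, power is about 94% unpaired against 95% paired at rho 0.1, and 98% against nearly 100% at rho 0.5. Alpha 0.0125 is set in 7a for sample size, and 8e does not say whether the correction extends to secondary outcomes. Time is capped at 2 minutes, so normal-theory figures are approximate.

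Much of this stands as a limit on size. The loss is small if rho is near 0.1 or if differences are about 1 SD or more. At alpha 0.05 the gap for 0.5 SD at rho 0.5 is still 54% against 81%.

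It does not rescue the text. Two of the four tests cannot be paired, and 8b does not ask for a paired form of the other two. The value 0.1 was chosen for a binary outcome, not for these three. Comparison across tourniquets is the natural reading and matches 8a. If the factor were a characteristic of the person and all five attempts were pooled, independence would still fail, and positive correlation would make standard errors too small. Calling the tests descriptive does not change the fact that they yield p-values.

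**Conclusion.** The concern holds. As written, section 8b prescribes independent-samples methods for repeated measurements, and nothing elsewhere in the plan corrects it. For comparisons between tourniquets the standard error is too large by 5%, 20%, 41% or 83% at rho 0.1, 0.3, 0.5 or 0.7. The power lost at 0.5 SD ranges from about 2 to 65 percentage points over that range. These sizes rest on an assumed positive rho, an illustrative difference and normal, equal-variance data; that pairing is ignored does not depend on them.

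The direction is conservative, and the McNemar analysis and the sample size of 34 are untouched. It should be corrected, but it ranks below a defect in the primary analysis.

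**What to change.** Rewrite section 8b so that each of the three outcomes is compared across tourniquets within participant:

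- Overall test: Friedman, or a linear mixed model with a participant random effect and fixed effects for tourniquet type and test position. The position term uses the randomised order to account for practice or fatigue. For time, the 2-minute cap may favour the rank-based route.
- Then four comparisons of CAT with each other tourniquet, by Wilcoxon signed rank or paired t-test, with the within-participant difference and its confidence interval.
- Name one method per outcome in advance, and state whether the Bonferroni rule in 8e applies to these comparisons (0.05 / 4 = 0.0125 if it does).
- Keep one-way ANOVA, Kruskal-Wallis, Mann-Whitney U and the two-sample t-test only for comparisons between different people, with one value per person.

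The cost is a change of SAP wording. The data are the same and no further participants are needed. It is best made before the secondary outcomes are analysed, so that the choice of test cannot follow the results.
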